7.8.3. Application of the Propensity Score

In the sections below, IPTW and PSM methods are described, and considerations for choosing IPTW as the primary analytical method, with PSM as an *a priori* sensitivity analysis are outlined. Propensity score weighting (e.g., IPTW) was chosen as the primary analytical method over PSM since IPTW would include all participants, rather than only those who are successfully matched. Successful matching can be challenging if the study cohort sample sizes are small and therefore, IPTW is recommended. Further, IPTW was chosen over other weighting methods (e.g., standardized mortality ratio weighting [SMRW]) and PSM since the target population is the entire study population, rather than the treatment population. Weighting methods are also subject to extreme weights, IPTW extreme weights can be reduced by using stabilizing weights. Finally, the treatment effect obtained after applying IPTW is referred to as the population ATE, while the resulting treatment effect obtained from SMRW is the average treatment effect on the treated (ATT) population. The ATE is more applicable for this study, since the Roctavian treatment may be offered to any participant eligible for the study and is not dependent on participant characteristics.³⁶ PSM is chosen as the *a priori* sensitivity analysis as it is commonly used in observational studies to balance the study groups while randomization is implausible. It provides subject-to-subject comparison by reducing the multi-dimensional covariate space to one dimension space and the results are easy to interpret.³⁷ As the primary analysis will utilize IPTW and PSM as an *a priori* sensitivity analysis, these approaches are summarized below in Table 7 and more details are provided around these approaches in Sections 7.8.3.1 and 7.8.3.2.

Presented below is a summary of considerations for the use of IPTW and PSM methods, described above.

Table 7: Considerations for IPTW versus PSM Methods

Propensity Score Method	Considerations
IPTW	
 • Includes all participants • Applies weights to both the treated and control cohorts • Estimates the ATE in the total study population • Subject to extreme weighting
PSM	
 • Only includes participants who are successfully matched • Successful matching can be challenging if the study cohort sample sizes are small • Analysis can be more interpretable to the scientific community as the inclusion of only matched participants mirrors randomized clinical trial designs

Abbreviations: ATE: average treatment effect; IPTW: inverse probability of treatment weighting; PSM: propensity score model.

7.8.3.1. Inverse Probability of Treatment Weighting

IPTW will be implemented to create a baseline reference of propensity score weights for comparison. Using this approach, each participant is assigned a weight representing the inverse probability of being assigned to their respective group. Thus, IPTW aims at giving more importance (i.e., more “weight”) to those participants that have unexpected propensity score values. For the treated group

(Roctavian Cohort), the weight, W , assigned in the IPTW method for each individual, i , based on propensity score, P_i , is:

$$W_i = \frac{1}{P_i}$$

For the control group (SoC Cohort), participants receive weights of:

$$W_i = \frac{1}{(1 - P_i)}$$

As the characteristics of the population that will be treated with Roctavian are unknown at the time of the SAP being drafted, it is possible that large differences in characteristics between the Roctavian and SoC Cohorts will exist. If this is the case, some participants may have extreme propensity score weights and, though representing a small portion of the observed population, have a disproportionate influence on the analysis. This outsized influence of individuals with extreme weights may increase variance and confidence intervals of the ATE estimate.³⁸

Stabilized weights can be used instead of the original, unstabilized weights. To calculate the stabilized weights, the numerator of the unstabilized weights is replaced by the marginal probability of receiving Roctavian and SoC in the overall sample. Additionally, weight values greater than five will be truncated to five due to the potential bias of outliers.^{39, 40}

For the Roctavian Cohort, the stabilized weight, W , assigned in the IPTW method for each individual i , is obtained by dividing the marginal probability of receiving Roctavian (i.e., a propensity score without considering covariates) P_T by individual's propensity score, P_i :

$$W_i = \frac{P_T}{P_i}$$

For the SoC Cohort, participants receive weights of:

$$W_i = \frac{(1 - P_T)}{(1 - P_i)}$$

We will conduct trimming of the nonoverlap regions of PS if extreme weights still exist with stabilized IPTW.^{41, 42} If the IPTW requires trimming due to extreme weighting to balance the propensity score distributions between the Roctavian and SoC Cohorts, and if the PSM sensitivity analysis can match a sufficient sample size to incorporate a 1:1 or 1:2 matching ratio (see Section 7.8.3.2 for details), the PSM approach will be reported as the primary analytical method for all analyses.

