7.6. Study Sample Size

The primary goal of HA treatment is to reduce the bleeding rate or to achieve freedom from bleeding. As an approximation of the appropriate number of cases for the data collection accompanying the application, the Institute for Quality and Efficiency in Health Care (IQWiG) conducted the sample size calculation based on ABR for treated bleeds. Evaluation of the ABR is performed using a negative binomial model.

The formula for The sample size calculation is as follows:

$$N_1 \geq \frac{(z_\alpha \sqrt{V_0} + z_\beta \sqrt{V_1})^2}{(\log(R_0) - \log(\lambda_2/\lambda_1))^2}$$

$$N_2 = \theta N_1$$

Where:

$$V_1 = \frac{1}{\mu_t} \left(\frac{1}{\lambda_1} + \frac{1}{\theta \lambda_2} \right) + \frac{(1 + \theta)\varphi}{\theta}$$

V_0 is computed using the fixed marginal total method, the 2nd method recommended by Zhu et al.:²⁷

$$V_{02} = \frac{(1 + R_0\theta)^2}{\mu_t R_0 \theta (\lambda_1 + \theta \lambda_2)} + \frac{(1 + \theta)\varphi}{\theta}$$

N_1 is the sample size for control, N_2 is the sample size for intervention. $\theta = \frac{N_2}{N_1}$, which is the sample size ratio; R_0 is the superiority margin ratio at the null hypothesis. In this case, R_0 is <1 since higher rates are worse. λ_1 is the event rate in the control group, and λ_2 is the event rate in the intervention group. φ is the dispersion parameter, and μ_t is the average exposure time. z_α is the z-score at the significance level, z_β is the z-score at the power value.

When higher rates are worse, the superiority by a margin test hypotheses are

$$H_0: \frac{\lambda_2}{\lambda_1} \geq R_0 \quad \text{vs.} \quad H_1: \frac{\lambda_2}{\lambda_1} < R_0$$

Where $R_0 < 1$.

The relative effect measure is the incidence rate ratio of Roctavian over SoC, which can be tested against the shifted null hypothesis of 0.5, assuming a significance level $\alpha = 2.5\%$ with a one-sided test, and power of at least 80%. Higher values for the ABR (parameter λ) stand for a worse outcome. Furthermore, a distribution of the Sample Roctavian vs. SoC of 1:5 is assumed (sample size ratio $\theta = 0.2$). Other required parameters are the Average Exposure Time ($u_t = 1$ year), the ABR for the SoC and Roctavian groups ($\lambda_{SoC} = 3$, $\lambda_{Roctavian} = 0.85$) and a value for the overdispersion ($\phi = 1.5$). This results in a total sample size of at least 397 participants (Roctavian Cohort $n = 67$, control Cohort $n = 330$).

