7.8.3.2. Propensity Score Matching

PSM will be considered *a priori* for a sensitivity analysis and initially be performed using the procedure of 1:4 matching. The PSM method matches each subject in the treated Cohort with four subjects in the SoC Cohort exhibiting the nearest propensity score (this is also known colloquially as 'greedy' matching) without replacement. Consequently, if all participants from the smallest group (i.e., Roctavian or SoC) are matched, then the sample size for the participants included in subsequent analysis becomes double the sample size of the smallest group of unpaired participants. If the appropriate matches are not available, for example due to a lack of overlap in propensity score values between groups, then cases are discarded and the matched sample size for analysis is reduced accordingly. For the PSM, a caliper width of 0.2 times the SD of the propensity score will be used and 'random' order.⁴³

If the 1:4 matching ratio is not achievable at the specified caliper with >90% of the Roctavian Cohort matched to four SoC participants, a 1:3 matching ratio will be attempted, followed by a 1:2 matching ratio and then a 1:1 matching ratio as needed based on the requirement to match >90% to the

relevant ratio. If the 1:1 matching ratio is not achievable, results for PSM will not be reported. Between IPTW and PSM, it is expected that one of these methods would have sufficient overlap and model fit to use for analyses, however if they don't, multivariable regression analyses with covariate adjustment will be conducted with discussion and agreement from the G-BA.

PSM will be conducted for the primary outcome and compared to the results using IPTW. If there is no notable difference in the primary outcome, only IPTW will be used for the secondary outcomes.

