more similar Roctavian and SoC Cohorts. Other clinically significant prognostic factors or covariates that remain imbalanced after propensity score adjustment will be included in the model as well. Regression coefficients, corresponding 95% CIs and p-values will be reported for all explanatory variables included in the model. The estimated rate ratio (ABR in Roctavian Cohort / ABR in SoC Cohort) generated from the IPTW weighted negative binomial model will be tested against the shifted null hypothesis of 0.5. For an alpha=0.025 test, the shifted null hypothesis is rejected if the upper boundary of the two-sided 95% CI for the rate ratio is less than the null hypothesis 0.5. The CI of the estimated rate ratio will be calculated using the Wald method.²⁷

Given some participants may have no treated bleeds based on prior literature,⁴⁶ a two-part zero-inflated negative binomial model will also be considered. If the negative binomial model does not converge,⁴⁷ or if the AIC in the model accounting for zero-inflation is lower, then the zero-inflation negative binomial model will become the primary objective analytic model, as lower AIC indicates a better fit. For the zero-inflated negative binomial model, first the model will be fit for a binary outcome whether a participant had a treated bleed during the outcome assessment period, and then an ABR count outcome for treated bleeds among participants who had at least one treated bleed during the outcome assessment period (excluding participants with zero bleeds) will be fit. Finally, the unconditional ABR estimates for treated bleed will be calculated by multiplying the estimated conditional ABR from the count model by the probability of having a treated bleed estimated from the binary model for both the Roctavian and SoC Cohorts.

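### The matched fallback in SAP 7.8.3.1 can become the primary analysis without the stated 80% power (for the test against 0.5) and without the target population that SAP 7.8.3 names

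*Protocol*

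**What the plan says.** SAP 7.8.3 makes IPTW primary and propensity score matching (PSM) the main sensitivity analysis. It gives two reasons: IPTW keeps all participants, and it was preferred to PSM "since the target population is the entire study population, rather than the treatment population". It calls the resulting effect the ATE.

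SAP 7.8.3.1 adds a contingency. Weights are stabilised and truncated at five. If extreme weights remain, the regions where the propensity scores do not overlap are trimmed. If trimming is required, and "if the PSM sensitivity analysis can match a sufficient sample size to incorporate a 1:1 or 1:2 matching ratio", then "the PSM approach will be reported as the primary analytical method for all analyses". The section does not say what follows if 1:3 or 1:4 is reached.

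SAP 7.8.3.2 and protocol 10.3.5.1 start at 1:4 and step down to 1:3, 1:2 and 1:1. Each ratio requires more than 90% of the Roctavian Cohort to be matched. SAP 7.8.3.2 notes that with full matching the analysed sample "becomes double the sample size of the smallest group of unpaired participants", which describes the 1:1 case.

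SAP 7.6 and protocol 10.1 size the study as two independent groups, SoC 330 and Roctavian 67, "with a one-sided test, and power of at least 80" per cent, for a rate ratio "which can be tested against the shifted null hypothesis of 0.5". "This results in a total sample size of at least 397 participants". No power is given for a matched set. SAP 7.9.3 then says that the rate ratio "generated from the IPTW weighted negative binomial model will be tested against the shifted null hypothesis of 0.5". Protocol 10.1 says instead that the nulls actually tested are not shifted, and protocol 10.3.6 names a two-sided two-sample t-test on mean ABR.

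**The concern.** Two things change when the fallback applies, and the plan mentions neither.

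The first is the target population. Matching SoC participants to Roctavian participants estimates the effect in matched Roctavian-type participants. The fallback therefore makes primary a method that SAP 7.8.3 passed over on exactly this ground. It does so when overlap is poor, which is when the two effects can differ most.

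The second is the amount of information. The more-than-90% rule protects the number of Roctavian participants kept but says nothing about SoC participants. A 1:1 match keeps 61 to 67 of 330 and drops 263 to 269 (330 - 67 = 263; 330 - 61 = 269). A true effect of the assumed size could then miss the 0.5 threshold because comparator data were set aside.

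**Working it through.** **Inputs (SAP 7.6).** SoC rate λ1 = 3, Roctavian rate λ2 = 0.85, dispersion φ = 1.5, null ratio R0 = 0.5, one-sided α = 0.025 (z = 1.960), mean exposure μ = 1 year, θ = N2/N1. Planned follow-up is 3 years, so μ = 3 is shown as well. More than 90% of 67 is more than 60.3, so at least 61 matched.

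**Formulae (SAP 7.6).**
- V1 = (1/μ)(1/λ1 + 1/(θλ2)) + (1+θ)φ/θ
- V02 = (1+R0θ)² / [μR0θ(λ1+θλ2)] + (1+θ)φ/θ
- D = log 0.5 - log(0.85/3) = 0.568
- Power = Φ{(√N1·D - 1.960·√V02)/√V1}

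**Reproducing the plan.** With θ = 0.2 and μ = 1, V1 = 15.216 and V02 = 12.817. Then N1 = (1.960·√12.817 + 0.842·√15.216)² / 0.3226 = 328.8. That is 329 SoC and 66 Roctavian, 395 in all, close to the stated 330, 67 and 397. At exactly 330:67, V1 = 15.016 and V02 = 12.655. The argument of Φ is (10.318 - 1.960·√12.655)/√15.016 = 0.863, so power is 80.6%.

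**1:1 matching, θ = 1, μ = 1.** V1 = 4.510 and V02 = 4.169.
- 67 pairs: (4.649 - 1.960·√4.169)/√4.510 = 0.305, power 62.0%.
- 61 pairs: (4.436 - 1.960·√4.169)/√4.510 = 0.205, power 58.1%.

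**All settings against R0 = 0.5.** The Wald columns replace V02 by V1, because SAP 7.9.3 names the Wald interval.

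| SoC:Roctavian | SAP formula, 1 y | SAP formula, 3 y | Wald, 1 y | Wald, 3 y |
|---|---|---|---|---|
| 330:67 (unmatched) | 80.6% | 89.1% | 75.9% | 87.7% |
| 268:67 (1:4) | 79.4% | 88.0% | 74.7% | 86.6% |
| 134:67 (1:2) | 73.0% | 82.2% | 68.9% | 80.8% |
| 122:61 (1:2) | 69.2% | 78.6% | 64.8% | 77.1% |
| 67:67 (1:1) | 62.0% | 71.1% | 59.1% | 70.0% |
| 61:61 (1:1) | 58.1% | 67.1% | 55.1% | 65.9% |

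Each entry should be read against the 330:67 row of its own column.

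**The other null.** With R0 = 1, as protocol 10.1 implies, 1:1 power is at least 99.6% in every setting. The t-test of protocol 10.3.6 at 1:1 gives 97% to 99% by normal approximation and above 99% by simulation (20,000 runs).

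**The case against.** A reader might infer that the fallback has only 55-71% power against a promised 80%. The documents do not support that as an unconditional statement.

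- The loss exists only for the test against 0.5 in SAP 7.9.3. Under protocol 10.1 or 10.3.6 the 1:1 comparison is not underpowered.
- The two ends of that range have different baselines. The 55.1% (61 pairs, Wald, 1 year) belongs with 75.9%, and the 71.1% (67 pairs, SAP formula, 3 years) with 89.1%.
- 1:1 is the last rung. At 1:2 with 67 sets and 3 years, power exceeds 80%.

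A reader might also infer that trimmed IPTW would have kept both the 80% and the ATE. It would not. SAP 7.8.3.1 itself says that extreme weights inflate the variance, and trimming also leaves the full population. As an illustration on an assumed figure, suppose weighting reduced the effective Roctavian size to 40 with 330 SoC kept. Then θ = 0.121, V1 = 23.91 and V02 = 19.86, and power at 1 year is 62.7%, about the same as 67 matched pairs.

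It is also fair that the hierarchy is prespecified, that its trigger uses covariates rather than outcomes, and that the stated 397 is correct for what it describes.

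These points limit the size of the problem but do not remove it. The plan's rule can still replace the primary analysis with one whose target population differs from the one SAP 7.8.3 chose, and whose power against 0.5 is stated nowhere.

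**Conclusion.** The point holds in a limited form. The conflict between SAP 7.8.3 and SAP 7.8.3.1 over the target population stands without any power assumption. The power shortfall is real for the SAP's test against 0.5 and is mainly a 1:1 problem: about 18 to 22 percentage points below the unmatched design on the SAP formula (80.6% to 62.0% or 58.1% at 1 year; 89.1% to 71.1% or 67.1% at 3 years). At 1:2 it is 69-73% at 1 year and 79-82% at 3 years (Wald 65-69% and 77-81%).

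The figures rest on the plan's rates and dispersion, on 61 to 67 matched Roctavian participants, and on treating matched sets as independent. Positive within-set correlation, for which the documents give no value, would raise power. Against an unshifted null there is no material shortfall, so the contradiction between protocol 10.1 and SAP 7.9.3 has to be settled before the power question has one answer. This should be corrected, but it does not invalidate the planned IPTW analysis.

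**What to change.** In SAP 7.8.3.1, when trimming would be needed, keep a weighted analysis primary using overlap weights, declare the overlap population as its target, and report PSM at the highest achievable ratio as the sensitivity analysis. This retains SoC participants whom a 1:1 match would discard. How much power it recovers depends on the overlap observed, which the documents cannot give.

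If the switch to PSM is kept:
- state in SAP 7.6 and protocol 10.1 that the 80% applies only to the unmatched 330:67 comparison;
- give the fallback power by ratio, as in the table above;
- state that the fallback estimates the effect in matched Roctavian-type participants, not the ATE.

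In either case, make protocol 10.1, protocol 10.3.6 and SAP 7.9.3 agree on the null. Protocol 10.3.5 fixes the method from the 18-month data cut, so this belongs before that cut.

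The cost is wording and one small table. The drawbacks are that the overlap population is also not the full-population ATE and must be named, and that the quoted fallback power is less favourable.

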7.8.3.2. Propensity Score Matching

PSM will be considered *a priori* for a sensitivity analysis and initially be performed using the procedure of 1:4 matching. The PSM method matches each subject in the treated Cohort with four subjects in the SoC Cohort exhibiting the nearest propensity score (this is also known colloquially as 'greedy' matching) without replacement. Consequently, if all participants from the smallest group (i.e., Roctavian or SoC) are matched, then the sample size for the participants included in subsequent analysis becomes double the sample size of the smallest group of unpaired participants. If the appropriate matches are not available, for example due to a lack of overlap in propensity score values between groups, then cases are discarded and the matched sample size for analysis is reduced accordingly. For the PSM, a caliper width of 0.2 times the SD of the propensity score will be used and 'random' order.⁴³

If the 1:4 matching ratio is not achievable at the specified caliper with >90% of the Roctavian Cohort matched to four SoC participants, a 1:3 matching ratio will be attempted, followed by a 1:2 matching ratio and then a 1:1 matching ratio as needed based on the requirement to match >90% to the

relevant ratio. If the 1:1 matching ratio is not achievable, results for PSM will not be reported. Between IPTW and PSM, it is expected that one of these methods would have sufficient overlap and model fit to use for analyses, however if they don't, multivariable regression analyses with covariate adjustment will be conducted with discussion and agreement from the G-BA.

PSM will be conducted for the primary outcome and compared to the results using IPTW. If there is no notable difference in the primary outcome, only IPTW will be used for the secondary outcomes.

7.8.3.3. Graphical Presentation of Propensity Score Diagnostics

The distribution of the propensity scores will be presented before and after weighting using histograms and density plots, and the c-statistic will be reported to visually assess any imbalance (i.e., to visually determine sufficient overlap between the two curves). Balance plots for the participant covariates included in the model will present the standardized differences before and after weighting and/or matching.

7.9. Statistical Analysis Approaches

Descriptive statistics will be generated for all study measures. Descriptive statistics will include means, 95% CIs, SDs, medians, interquartile range (IQR), and minimum and maximum values for continuous variables and frequencies and percentages for the categorical variables. Univariate statistics will be calculated for each measure of interest. Baseline and outcome variables will be compared between the Roctavian and SoC Cohorts using chi-square tests for categorical variables, two-sided t-tests for continuous variables, and Wilcoxon rank-sum tests for medians of continuous variables if the continuous variables are not normally distributed.

For event-based outcomes including the bleeding outcomes, negative binomial models will be fit. Zero-inflated negative binomial models will also be considered if the outcomes show excess zeros (see Section 7.9.3 for details). For binary outcomes, logistic regressions will be fit. For continuous outcomes, general linear regression will be used, with appropriate transformation if needed to ensure model assumptions are met. For COAs, general linear mixed models to account for repeated measures are planned. All the models will be adjusted with propensity score weights and results will be reported based on observed values (before IPTW is applied) and the weighted values (after IPTW is applied).

To adjust for confounding, propensity scores will be calculated and applied using appropriate propensity score IPTW to ensure balance of covariates between the Roctavian and SoC Cohorts. Both unadjusted and propensity score adjusted results will be reported. IPTW is the primary propensity score method for adjustment of confounding. PSM will be performed as an *a priori* sensitivity analysis. Additional details on propensity score methodology is presented in Section 7.8. If additional covariate adjustment is required to balance the Cohorts, multivariable models will be reported.

P-values and SMDs will be reported for comparisons between Roctavian and SoC Cohorts. A p-value <0.05 will be considered statistically significant. All analyses will be based on observed, not projected, data. The sample size calculations are powered for the primary outcome (i.e., ABR), therefore, all p-values associated with secondary outcomes are nominal.

